5.5 Duration of the intervention period and frequency of follow up

The trial duration per participant is 28 days. Participants will complete assessments at baseline and daily after baseline. Respiratory status of patients will be assessed every 4 hours for the first week, and then daily. The appendix provides a summary of the times at which data are collected.

For historical controls, data will be collected where available for 28 days from the date of admission to hospital. See section 7.5.1 of the protocol for more details.

6 Data analysis plan

6.1 General statistical considerations

All analyses will be descriptive in nature and should be considered as hypothesis generating rather than providing firm conclusions. All statistical tests and confidence intervals will be 2-sided. Significance will be considered at the 5% level and confidence intervals will be at the 95% level.

Analyses for both primary and secondary outcomes will be conducted following an Intention To Treat (ITT) approach, and non-compliance will be reported at the individual patient level. No adjustments for missing data will be made.

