## 10.5 Randomisation methods

No randomisation will be employed in this pilot study due to practical and ethical considerations.

A statistically powered RCT would be ideal to define the magnitude of benefit and impact on overall survival and is the typical design in patients with ARDS. Although there is clinical data on the safety of nebulised rtPA, but there are no clinical data on this condition to facilitate a sample size calculation. There are data from a small RCT that has used another fibrinolytic agent, but the doses are not comparable (Abdelaal Ahmed Mahmoud et al. 2020). If a patient is randomised to receive no treatment, this precludes participation in other interventional studies which might increase the risk of mortality. The most recent figures suggest a 50% mortality in patients receiving

IMV. (<https://www.icnarc.org/About/Latest-News/2020/04/04/Report-On-2249-Patients-Critically-III-With-Covid-19>) Currently there is a concerted effort to introduce multiple therapies based on our understanding of the pathophysiologic basis of disorder. Ethical concerns were raised about the potential for denying patients new treatment strategies when randomised to standard of care arm. The management strategies are evolving on an unprecedented scale with repurposing of existing medications, many of which are proof of concept of studies. Further, if this pilot study shows significant effect in a subset of patients, there would be justification to progress to a statistically powered RCT. We would progress to a RCT only after submission of a substantial amendment to this trial protocol or submission of a new clinical trial application. In the event of major adverse drug reactions or minor improvement in the oxygenation as assessed by  $\text{PaO}_2/\text{FiO}_2$ , there are minimal gains to be had with a larger randomised control study.

A Data Monitoring Committee (DMC) will be set-up to review safety data within the trial along with the final study results and advise on progressing from a pilot study to a statistically powered RCT based on the safety and efficacy data that is collected.

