### **10.6.2 Primary outcome analysis**

The PaO2/FiO2 ratio measured over time will be described for each group. The change from baseline in the PaO2/FiO2 ratio will be summarised at each post baseline timepoint. Plots will be used, where appropriate, to show the PaO2/FiO2 summarised for patients over time.

PaO2/FiO2 will be a calculated field on the trial database derived from the fields for PaO2 and FiO2. For cohort 2 data will be extracted once a day coinciding with the worst PF ratio. As PF ratio is the primary endpoint, in addition to the worst PF ratio, up to a maximum of 6 data points spread across 24 hrs that represents patients clinical status will be extracted. Details of further data derivation and analyses will be described in the SAP.

All patient data will be used, regardless of any intercurrent events that may have occurred after enrolment:

- Data from patients recruited into the rtPA + SOC group will be summarised whether or not patients have received all planned doses of the IMP.
- Any change in requirement for oxygenation and ventilation support will be summarised and described
- Changes in PaO2/FiO2 ratio over time will be described and interpreted taking into consideration that a patient's condition may have changed and led to their ventilation type changed post enrolment. If data allows, additional descriptions of the PaO2/FiO2 ratio over time may be performed in each subgroup of patients experiencing such changes (e.g. IMV to NIV, or vice versa).

The incidence and severity of bleeding events will be summarised in each group, and the change in fibrinogen levels will also be summarised at each post-baseline timepoint.

For cohort 1, subject to the final sample size and data quality, outcomes will also be compared between the SOC only group and intervention (rtPA + SOC) group using appropriate regression methods to make adjustment for baseline characteristics. Appropriate data transformations required for model assumptions will be considered if necessary.

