6.3 Analysis of primary outcome

The primary outcome for efficacy is oxygenation, measured using the PaO₂/FiO₂ ratio over time. The distributions of the primary outcomes will be summarised, by group, over time. Change in PaO₂/FiO₂ ratio from baseline will be checked visually using means & SE plots. If necessary, appropriate transformations of the data will be performed (e.g., using the natural logarithm).

Subject to the final sample size and data quality, PaO₂/FiO₂ ratio will also be compared between the SOC group (historical controls) and rtPA group using appropriate regression modelling, controlling for baseline oxygenation ratio:

$$OXY_i = \beta_0 + \beta_1 \cdot T_i + \beta_2 \cdot OXY0_i + \varepsilon_i,$$

where the i subscript denotes the i^{th} patient and

- OXY_i = PaO₂/FiO₂ ratio (oxygenation) at the end of treatment;
- T_i = group indicator (= 1 if patient is in the rtPA group, = 0 otherwise);
- $OXY0_i$ = PaO₂/FiO₂ ratio (oxygenation) at baseline;
- $\varepsilon_i \sim N(0, \sigma^2)$ = Normally distributed error term.

The estimate of the parameter β_1 and associated 95% confidence interval shall be reported, as well as a p-value pertaining to the hypothesis test of

$$H_0: \beta_1 = 0 \text{ versus } H_1: \beta_1 \neq 0.$$

Similarly, the use of models using oxygenation at other meaningful timepoints as outcome measure will be evaluated. Owing to a limited sample size, models shall not adjust for other baseline characteristics. Fitted models shall be checked, where appropriate, to ensure that modelling assumptions have been satisfied. Appropriate transformations of outcomes or other suitable approaches (e.g., robust or non-parametric methods) shall be explored if model assumptions are not satisfied.

For treatment safety, the incidence and severity (either major or minor) of bleeding events will be summarised with frequencies and percentages in each group. Fibrinogen levels will also be summarised graphically using plots of the mean, by group, over time. Finally, the number and nature of serious adverse events (SAEs) will be summarised. These events are defined in section 8 of the protocol.

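### The SAP claims ITT but has no rule for PaO2/FiO2 after death or discharge, so later comparisons cover only patients alive in hospital and can be biased in either direction

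*SAP*

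**What the plan says.** SAP 6.1 sets the principle: "Analyses for both primary and secondary outcomes will be conducted following an Intention To Treat (ITT) approach". The same section then states "No adjustments for missing data will be made", and sets two-sided tests at 5% with 95% intervals.

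SAP 6.3 specifies one comparison, a linear regression of a single P/F value per patient, "ratio (oxygenation) at the end of treatment", on group and baseline P/F. It reports the group coefficient with a confidence interval and a p-value. Models at other timepoints are to be evaluated. The primary endpoint (Protocol 10.1.1) also covers daily values and values 3 and 5 days after treatment ends.

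SAP 4 ends follow-up at discharge, death or day 28. Protocol 10.6.2 says "All patient data will be used, regardless of any intercurrent events that may have occurred after enrolment", but the bullets beneath it deal with incomplete dosing and changes of respiratory support, not with death or discharge. Protocol 10.6.4 leaves sensitivity analyses to the SAPs. The SAP contents page lists such a section, but the body has none.

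**The concern.** P/F does not exist after death and is not collected after discharge. A patient without a value cannot enter the regression or the summary at that timepoint, so what is compared is the patients who remain. Deaths tend to remove low values and discharges high ones. A treatment that changes either changes who is measured, quite apart from any effect on oxygenation.

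Losses could be heavy. On mortality, Protocol 10.5 says "The most recent figures suggest a 50% mortality in patients receiving" IMV, and Protocol 2.1 gives 25 to 60% for ARDS under standard care. The groups also differ by design: controls who died early are excluded (within 48 hours of admission in Protocol 10.4.2, within 2 to 3 days in SAP 4), and treated patients have no matching rule.

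The P/F result has a use. Protocol 10.5 says that a minor improvement in oxygenation would leave little to gain from a larger trial, and under Protocol 12.2 the DMC advises on progression from these data.

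**Working it through.** **The plan's own figures.** There is no effect size, SD or power to reproduce. The allocation arithmetic agrees: 12 + 24 = 36 planned, and 9 treated at 1:2 give 18 controls (Protocol 4.1).

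**Where values are lost.**
- Later fixed days, and 3 and 5 days post treatment: a patient who has died or gone home has no value. The loss is certain.
- End of treatment: not defined for a patient who dies on treatment. If it means the last on-treatment value, that patient may still have one.
- Controls: they have no treatment and so no end of treatment. SAP 6.2 takes their baseline as the last value before enrolment as defined in a section 8.2, but Protocol 8.2 concerns adverse-event recording.

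**Check 1: closed form, no true P/F effect.** Assumptions, not in the documents: normal P/F, SD 80 mmHg, deaths falling on the lowest values. With mortality p, the mean of survivors in SD units is λ(p) = φ(z_p)/(1 − p). This gives λ(0.3) = 0.497, λ(0.5) = 0.798 and λ(0.7) = 1.159.
- Control 50%, rtPA 30%: (0.497 − 0.798) × 80 ≈ −24 mmHg.
- Control 50%, rtPA 70%: (1.159 − 0.798) × 80 ≈ +29 mmHg.
- If death tracks P/F half as closely: −12 and +14 mmHg.

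Precision at 9 v 18: the survivor variance in SD² units is 1 + z_pλ − λ², giving SDs of 56.2, 48.2 and 41.1 mmHg at 30%, 50% and 70% mortality. Expected survivors are 9 controls and 6.3 or 2.7 treated.
- 30% on rtPA: √(48.2²/9 + 56.2²/6.3) ≈ 28 mmHg.
- 70% on rtPA: √(48.2²/9 + 41.1²/2.7) ≈ 30 mmHg.

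Both spurious differences lie within about one standard error.

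**Check 2: simulation of the SAP 6.3 model in survivors, 9 v 18.** Assumptions: P/F mean 200, SD 70, correlation 0.5 with baseline, patients with lower P/F more likely to die; 1,500 runs per scenario. The last column is the probability that a treated patient ranks above a control when everyone is kept and death ranks worst; values above 0.5 favour rtPA.

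| True shift (mmHg) | Mortality, control v rtPA | Mean group coefficient (mmHg) | Death-worst rank |
|---|---|---|---|
| 0 | 50% v 50% | −0.2 | 0.503 |
| 0 | 50% v 25% | −20.1 | 0.580 |
| 0 | 25% v 50% | +20.7 | 0.430 |
| +20 | 50% v 50% | +19.0 | 0.531 |
| +20 | 50% v 40% | +12.5 | 0.571 |
| +20 | 50% v 25% | +0.5 | 0.616 |
| +20 | 50% v 10% | −10.8 | 0.657 |
| +20 | 25% v 50% | +39.9 | 0.470 |
| +30 | 50% v 10% | 0.0 | 0.682 |

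Adjusting for baseline P/F does not remove the bias. At 50% mortality in both groups, about half of the 27 patients are analysed. The planned 12 v 24 shows the same pattern (true +20, 50% v 10%: −11.6).

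**Check 3: discharge, no true effect.** If the best 40% of treated and 20% of control patients are missing through discharge, the coefficient is −14.4 mmHg. At 50% v 20% it is −22.8 mmHg.

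**The case against.** A reader might infer three stronger things, and the documents support none of them.

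- That patients are dropped silently. SAP 6.2 requires a flow chart by group with discontinuations (death is named), numbers analysed, and exclusions with reasons. Protocol 10.6 requires the number of observations with each continuous summary. In-hospital mortality is a secondary outcome, and the daily ordinal scale has death as its worst category. What is missing is the split into dead and discharged at each P/F timepoint.
- That the specified model necessarily excludes everyone who dies. Respiratory data are extracted at least daily (Protocol 7.5.1), so a last on-treatment value may exist. Treatment may stop after 48 hours of maintained saturation on room air (Protocol 7.3.3), so end of treatment can also precede discharge.
- That the sign is likely to be wrong. A gap of 50% v 40% only attenuates a +20 mmHg effect, and a +30 mmHg effect is cancelled rather than clearly reversed at 50% v 10%. The closed-form figures assume no true effect, so they show spurious differences, not reversals.

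It is also fair to say that the 50% figure is for IMV patients only, and that the calculations assume every death precedes the measurement. Protocol 2.7.4 shows biomarker samples from 9 of 9 treated patients at day 3, 8 at day 5 and 2 at day 13, without reasons, so heavy early loss in the treated group is not evident. The comparison itself is conditional ("Subject to the final sample size and data quality"), confined to cohort 1 and labelled hypothesis generating.

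These points limit the size and the stakes. They do not supply a rule for death or discharge, and reporting mortality in another table does not correct the P/F coefficient.

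**Conclusion.** The concern stands in limited form. The ITT label does not fit an analysis that has no provision for death or discharge. At later fixed days and at 3 and 5 days post treatment, the P/F results describe patients alive in hospital. At end of treatment the same may hold, and for controls that timepoint has no meaning.

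Mortality gaps of 20 to 25 percentage points give spurious differences of roughly 10 to 30 mmHg in either direction. Reversal of a real effect is possible but needs a larger gap, such as 50% v 10% with a true +20 mmHg. All sizes rest on an assumed SD of 70 to 80 mmHg and an assumed link between low P/F and death; the documents give neither. The bias is about one standard error or less, so in a single small dataset it could not be told from chance. That is a reason to report in a way that exposes it, given that the result informs the decision on a randomised trial.

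**What to change.** Amend the SAP as follows.

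1. Keep the planned regression, but call it an analysis of patients alive in hospital with a P/F value, not ITT.
2. Add one supportive rank analysis at a fixed day, for example day 7: death ranked worst, discharge alive off oxygen ranked best, everyone else ordered by P/F. Stratify by ventilation type and combine the strata into one result. The non-invasive stratum alone is 3 v 6, with 84 possible arrangements, so the smallest two-sided p-values are 2/84 = 0.024 and 4/84 = 0.048; only complete or nearly complete separation could reach 5%.
3. Define a time zero for controls equivalent to first dose, and replace the section 8.2 reference. Day 7 cannot be placed without it.
4. Reconcile 48 hours with 2 to 3 days, and apply the same early-death exclusion, counted from the same time zero, to both groups in the rank analysis. Otherwise ranking death worst favours the controls.
5. At each P/F timepoint, show by group the numbers alive in hospital with a value, dead and discharged.

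The cost is a few SAP lines and one more exploratory analysis. Its result has no mmHg unit and will be imprecise at 9 v 18. Neither treatment nor data collection changes.

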6.2 Summary of baseline characteristics

All baseline covariates and baseline valued of the outcomes will be summarised using descriptive statistics. For patients treated with rtPA + SOC, the last available value prior to the first administration of IMP will be considered the baseline value. For historical controls receiving SOC only, the last available value prior to enrolment, as defined in section 8.2, will be considered the baseline value. Categorical variables shall be reported as frequencies and percentages. Reports of continuous variables shall include mean or median and standard deviation or interquartile range (IQR) as appropriate, as well as minimum and maximum values.

Summary measures for the baseline characteristics will be presented both overall and by group. We will compare baseline characteristics visually to assess whether balance has been achieved. No significance testing will be used. The number of missing observations will be reported.

A CONSORT flow chart will be provided (Schulz et al., 2010). This will include the number of eligible participants, number of participants agreeing to enter the trial, then by intervention arm: the number of patients in each group that were enrolled, assessed for eligibility, excluded (with reasons listed), assigned to a group, treated with rtPA, followed up, discontinued (with reasons such as lost to follow-up, withdrawn, or death), and number of patients analysed in each group, and where applicable excluded from analyses (with reasons).

6.3 Analysis of primary outcome

The primary outcome for efficacy is oxygenation, measured using the PaO₂/FiO₂ ratio over time. The distributions of the primary outcomes will be summarised, by group, over time. Change in PaO₂/FiO₂ ratio from baseline will be checked visually using means & SE plots. If necessary, appropriate transformations of the data will be performed (e.g., using the natural logarithm).

Subject to the final sample size and data quality, PaO₂/FiO₂ ratio will also be compared between the SOC group (historical controls) and rtPA group using appropriate regression modelling, controlling for baseline oxygenation ratio:

$$OXY_i = \beta_0 + \beta_1 \cdot T_i + \beta_2 \cdot OXY0_i + \varepsilon_i,$$

where the i subscript denotes the i^{th} patient and

- OXY_i = PaO₂/FiO₂ ratio (oxygenation) at the end of treatment;
- T_i = group indicator (= 1 if patient is in the rtPA group, = 0 otherwise);
- $OXY0_i$ = PaO₂/FiO₂ ratio (oxygenation) at baseline;
- $\varepsilon_i \sim N(0, \sigma^2)$ = Normally distributed error term.

The estimate of the parameter β_1 and associated 95% confidence interval shall be reported, as well as a p-value pertaining to the hypothesis test of

$$H_0: \beta_1 = 0 \text{ versus } H_1: \beta_1 \neq 0.$$

Similarly, the use of models using oxygenation at other meaningful timepoints as outcome measure will be evaluated. Owing to a limited sample size, models shall not adjust for other baseline characteristics. Fitted models shall be checked, where appropriate, to ensure that modelling assumptions have been satisfied. Appropriate transformations of outcomes or other suitable approaches (e.g., robust or non-parametric methods) shall be explored if model assumptions are not satisfied.

For treatment safety, the incidence and severity (either major or minor) of bleeding events will be summarised with frequencies and percentages in each group. Fibrinogen levels will also be summarised graphically using plots of the mean, by group, over time. Finally, the number and nature of serious adverse events (SAEs) will be summarised. These events are defined in section 8 of the protocol.

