### 7.3 Treatment Schedule for nebulisation

Patients in the rtPA and SOC group will receive the first dose as soon as possible after enrolment, and in accordance with the dosing schedule below. The time of initiation of the first dose will be recorded and the timing of the initiation of subsequent doses will be relative to this time. 10mg rtPA will be administered by nebulisation every 6 hours. Treatment with rtPA will be administered at a dose of 10 mg every 6hrs for a minimum of 5 days initially and a maximum of 14 treatment days overall.

#### 7.3.1 Cohort 1

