### 7.3.3 Treatment discontinuation

Treatment may be stopped at any point in a patient if any of the following rules are met:

- If plasma fibrinogen levels fall to <1.0 g/L, the further dosing of rtPA in the patient will be stopped (see section 7.4).
- Patient maintains saturation on room air that is either normal or normal for them for 48 hours as assessed by the investigator
- A trial stopping rule has been met (see section 7.10)

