### 7.3.4 Re-treatment with rtPA after treatment discontinuation due to improvement in patient saturation (as described above)

If there is a recurrence of COVID-19 ARDS related symptoms or a worsening of PaO2/FiO2 ratio, which the investigator considers could be related to treatment discontinuation, treatment can be restarted. The decision to re-treat will be made within 5 days (120 hrs) from the last dose of treatment. Treatment may not be restarted more than once.

The rationale for restarting of treatment must be documented in the notes, along with the absence of toxicity. The patients monitoring will done according to main treatment phase.

### 7.3.5 Re-treatment of patients previously consented and treated on the trial – Cohort 1

For patients that have already been treated under the previous 3 day dosing schedule, if they remain eligible for the trial, they will be offered the option to continue treatment as above – the maximum number of days of extra treatment for these patients will be 11 days. Patients (or their legal representatives) must give consent to this re-treatment.

The total duration of trial participation for these patients may exceed 28 days (to approximately 5-6 weeks) to allow us to extend treatment to the maximum 14 days and to allow us to collect 5 days of post treatment data. We will inform the patient or their legal representative of this possibility and this will be documented in the patient information sheet.

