## 8.5 Notification of deaths

Only deaths assessed as likely related to IMP administration will be reported to Sponsor, see section 9.4 above.

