### **10.6.1 Summary of baseline data and flow of participants**

All pre-treatment assessments data in the protocol will be listed and all relevant data will be tabulated for each group separately.

For patients treated with rtPA + SOC, the last available value prior to the first administration of IMP will be considered the baseline value.

For patients receiving SOC only (historical controls), the last available value prior to enrolment, as defined in section 8.2, will be considered the baseline value.

All data necessary to produce a consort flow diagram (<http://www.consort-statement.org/>) will be summarised: the number of patients in each group that were enrolled, assessed for eligibility, excluded (with reasons listed), assigned to a group, treated with rtPA + SOC, followed up, discontinued (with reasons such as lost to follow-up, withdrawn, or death), and number of patients analysed in each group, and where applicable excluded from analyses (with reasons).

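### The written-out between-group model in SAP 6.3 uses P/F at end of treatment, a day that varies in rtPA patients and does not exist for historical controls, whose baseline is also undated

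*SAP*

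**What the plan says.** SAP 6.3 regresses one P/F value per patient on group and baseline P/F. The outcome is the "ratio (oxygenation) at the end of treatment". A 95% CI and a p-value for the group coefficient (β1) are to be reported. Models at other meaningful timepoints will be evaluated, but none is named.

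**rtPA patients, cohort 1**
- Protocol 7.3 gives treatment "for a minimum of 5 days initially and a maximum of 14 treatment days overall".
- Protocol 7.3.3 allows an individual stop if "Patient maintains saturation on room air that is either normal or normal for them for 48 hours as assessed by the investigator".
- Protocol 7.3.4 allows treatment to resume after such a stop: "Treatment may not be restarted more than once".
- Protocol 7.3.5 offers further treatment "For patients that have already been treated under the previous 3 day dosing schedule".

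**Historical controls**
- SAP 6.2: "For historical controls receiving SOC only, the last available value prior to enrolment, as defined in section 8.2, will be considered the baseline value". Protocol 10.6.1 has the same rule: "the last available value prior to enrolment, as defined in section 8.2, will be considered the baseline value".
- Protocol 8.2 covers adverse event recording, and the SAP has no section 8.2.
- Enrolment is described in Protocol 7.2, where it follows consent. Protocol 6.4 says consent is not sought from controls.
- SAP 4 matches on P/F from admission data without giving a day.
- Day 7 for SOC patients, in footnote a of both schedules of assessments, marks the end of frequent data extraction. It is the counterpart of 5 days after the last dose, not of end of treatment.

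**The concern.** The model has no term for the day of measurement. If P/F drifts on average, reading the two groups at different distances from baseline moves β1 even when the drug does nothing. If good oxygenation can itself end treatment, the rtPA reading day is chosen partly by the outcome, while the control day is chosen by the analyst. The confidence interval reflects sampling error only and would show neither effect.

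What is at stake is the use made of β1. Protocol 2.5 says the controls were recruited to evaluate efficacy so that a phase 3 sample size could be calculated. A shifted β1 could enter that calculation as an effect estimate.

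**Working it through.** **How far the end day can vary.** From the cohort 1 schedule (Protocol 7.3.1): 4 doses/day x 5 days = 20 doses, the last at 19 x 6 = 114 h. 4 x 14 = 56 doses, the last at 55 x 6 = 330 h. The difference is 216 h, or 9 days. The earlier 3-day schedule gives 12 doses, the last at 66 h.

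**Is there a control date?** The reference to section 8.2 is probably a numbering slip for 7.2. Protocol 8.5 shows the same offset: "Only deaths assessed as likely related to IMP administration will be reported to Sponsor, see section 9.4 above", where the procedure meant is now in 8.4. Reading 7.2 for 8.2 does not help, because enrolment there requires consent. Neither the control baseline nor the control outcome can be dated from the text.

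**Algebra when the end day is unrelated to P/F.** Let y = a + b x baseline + s x d, where d is days from baseline to reading and s is the mean trend. With no drug effect and comparable baselines, omitting d gives

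E(β1) = s x (mean d in rtPA - mean d in controls).

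Example: rtPA ends uniform on days 5 to 14 have mean 9.5. With s = 5 mmHg/day (assumed) and controls read at day 7, 5 x 2.5 = +12.5; at day 14, 5 x (-4.5) = -22.5. Simulating the SAP model (9 vs 18; assumed baseline SD 50, residual SD 60, slope on baseline 0.5; 3000 runs) gave +12.2 and -22.4.

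**When stopping depends on P/F, that formula is not enough.** Assumed rule: stop once P/F is at least 300 on two consecutive days from day 5, otherwise day 14 (start 150, SD 40; individual slope SD 12; daily SD 30).
- Trend +5, controls at day 7: formula +28.7, simulated +9.5.
- Trend +5, controls read at the rounded mean rtPA day (gap 0): formula 0, simulated -15.4.
- Flat trend: formula 0, simulated -9.7 to -12.9, depending on the control day.
- Same stopping rule applied to both groups: within 1.5 of zero.

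**Range under a second set of assumptions.** No drug effect, 9 vs 18, start 150 (SD 40), trend 4 or 8 mmHg/day, slope SD 8 or 12, daily SD 30, early stop after 48 h at P/F of at least 340, 4000 replicates. Entries are mean β1 in mmHg, with rejection at 5% in brackets.

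| rtPA ends | Controls at day 7 | Controls at day 14 |
|---|---|---|
| Spread over days 5-14 | +8 to +19 (7.2-10.7%) | -18 to -41 (3.8-10.7%) |
| Planned to day 14 | +17 to +49 (10.9-32.2%) | -3 to -19 (4.1-4.6%) |
| All day 5 | -8 to -16 (4.4-7.5%) | -36 to -73 (4.4-35.1%) |

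The mean model SE is 26.5 to 69.2. With a flat trend the shift is within 2.2 mmHg in 10 of 12 settings and about -6 in the two with treatment planned to day 14 and slope SD 12.

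**After the fix.** At 144 h from a common origin in both groups, mean β1 is -0.2 to +0.8, rejection 4.5-5.8%, SE 25.3-33.8.

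**Why the origin matters too.** Suppose P/F falls 4 (or 8) mmHg/day to day 5 after admission and then rises at that rate, and controls are timed from admission. Reading 144 h after each group's own start gives +14.5 (+28.0) if rtPA starts 2 days after admission and +38.1 (+76.5) if it starts 5 days after. With an aligned index the shift is within 0.6.

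**The case against.** This is one comparison, made only if sample size and data quality allow, within cohort 1 (9 rtPA patients and 18 controls, Protocol 4.1). Both documents call the analyses descriptive and hypothesis generating. By-group summaries over time and models at other timepoints are also planned. Progression to an RCT is a DMC judgement on safety and efficacy together, not a test on β1. Every simulated figure rests on trends and SDs that the documents do not give, and the day 7 and day 14 control readings are assumptions as well. All of this stands and limits the severity. It does not supply the missing control day: unnamed timepoints would still have no origin in controls.

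Three stronger readings are tempting.
- A reader might infer that the bias is simply trend times gap, so that equal planned days or a flat trend would remove it. The room-air stopping rule prevents that conclusion, as the zero-gap and flat-trend results show.
- A reader might infer that the model favours rtPA. The sign depends on the unknown trend and on the control day picked.
- A reader might infer that controls will be read at day 7. The documents use that day only to limit data extraction and assessments.

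The remedy is also open to objection. Protocol 2.5 reports preliminary oxygenation findings, and Protocol 4.1 says cohort 2 was shaped by analysis of cohort 1, so a new outcome time is now post hoc. Controls were matched on P/F at an undated point in admission, so the severity match may not hold at a new index. Deaths were assumed at only 7-10% when the 144 h analysis was tested with deaths left out (bias at most 1.1 mmHg), whereas the protocol cites 50% mortality on IMV and 6 of the 9 rtPA patients were on IMV. These points belong in the fix as stated costs.

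**Conclusion.** The point holds and should be fixed. As written, neither the outcome nor the baseline in the SAP 6.3 model can be dated for controls. Whatever control day is chosen, β1 mixes drug effect with days since baseline and with outcome-dependent stopping.

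The documents do not determine the size or the sign. Under the assumed trends of 4 to 8 mmHg/day, most shifts are below or near one model SE, and rejection under no effect ranges from about 4% to 35%. With a flat mean trend the shift is usually near zero but reached about -6 to -13 mmHg where stopping depended strongly on P/F. The documents do not show that the comparison will mislead; they show that it is not fully specified and that its interval would not reveal the problem.

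**What to change.** 1. **Index time and baseline (SAP 6.2-6.3, Protocol 10.6.1).** Replace the section 8.2 reference with one dated index time per control, for example the matched rtPA patient's time from hospital admission to first dose; admission is recorded in both groups (Protocol 7.5.2 and 7.7.2). Take baseline as the last P/F before first dose or index. Reconcile this with the SAP Study Summary, which defines baseline as 3 days prior to treatment. Report P/F balance at the index.
2. **Outcome (SAP 6.3).** Define it in both groups as P/F at one fixed time after first dose or index, with a stated window. An example is 144 h, which SAP 5.2 already uses as day 7 for lung compliance. Extract control P/F to that time. This fits the 28-day control collection if the index is within 28 - 6 = 22 days of admission.
3. **Deaths and discharges.** Report both before that time by group, with a sensitivity analysis that ranks deaths worst. SAP 6.1 makes no adjustment for missing data, so state what is done when the window holds no value.
4. **End-of-treatment P/F.** Keep it as description within the rtPA group, and say which end counts after a restart.

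**Cost.** The change is wording plus a date derived from data already collected. It must be documented and justified as post hoc, which SAP 2.1 permits. Some of the 18 controls may not be usable at their index. For 9 vs 14, SE rises by sqrt[(1/9 + 1/14)/(1/9 + 1/18)] = 1.047, about 5%; for 9 vs 9, by 1.155, about 15%. Any redraw must respect the data-sharing notices, which Protocol 6.4 says end on 31 March 2021. Effects after the fixed time, and differences in treatment received by then, are left to the over-time summaries.
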